### **8.7 Heterogeneity Among Investigational Sites**

An objective of this study is to evaluate variability in outcome among ‘real world’ users. To this end, an evaluation of heterogeneity among investigational sites may be important for this evaluation. Key summary adverse event endpoints such the per subject occurrence of any serious event, any device-related event, and any serious device-related event will be stratified by investigational site. If there is sufficient data, the site stratified event rates will be subjected to a random effects analysis on arcsine transformed proportions. Sites contributing fewer than 5 subjects will be pooled. True site-effects are assumed to be normally distributed with mean  $M$  and variance  $t^2$ . By imposing a specified distribution on the site-to-site variability, i.e., a normal distribution with mean  $M$  and variance  $t^2$ , sensitivity to small sample sizes in individual sites is reduced, and the parameters reflecting the magnitude of site-to-site variability are naturally derived. The quantitative measure of the magnitude of heterogeneity is  $I^2$ .  $I^2$  is the fraction of total site-to-site variance that is due to event rate heterogeneity across sites, as opposed to sampling variance. If  $\sigma^2$  is the total variance, then  $I^2 = t^2 / \sigma^2$ . Fractions of 25% and less are considered small and not clinically significant (Higgins and Thompson 2002). Site variability will be visually evaluated using a Forrest plot. If these analyses reveal specific sites that are outliers, further quantitative and qualitative analyses will be performed to investigate potential reasons.

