## 8.2 Evaluation of Periprocedural Events

The rates of all adverse events occurring within 24 hours post procedure and hospital discharge status for all opened devices at each participating clinical site during the surveillance period will be summarized. Adverse events of special interest include vessel perforation or dissection, intracranial aneurysm rupture, stroke, hemorrhage, death, inability to deploy or remove the device, and coil entanglement. The numbers of individual adverse events of each type and the per subject incidence rate for each type of adverse event will be determined and reported along with 90% two-sided exact binomial confidence intervals. The upper bounds of 90% two-sided exact binomial confidence intervals are equivalent to the upper bounds of 95% one-sided exact binomial confidence intervals. While the estimated incidence rates for each type of adverse event will be taken as the most likely value of the true incidence rate, the corresponding upper bound of the one-sided 95% exact binomial confidence interval will be taken as the largest possible incidence rate consistent with the observed sample results.

Separate event counts and incidence rates with corresponding confidence intervals will be summarized for adverse events determined to be serious, device-related, serious and device-related, procedure-related, serious and procedure-related, and severe. Listings for all adverse events will be compiled that provide full descriptions of each adverse event including determination of the severity, seriousness, and relationship to the device or procedure. The following listings will be compiled:

- AE Listing 1 All AEs Sorted by Event Type
- AE Listing 2 All AEs Sorted by Subject and Relative Time of Onset
- AE Listing 3 Serious AEs
- AE Listing 4 Severe AEs
- AE Listing 5 Device-Related AEs
- AE Listing 6 Procedure-Related AEs
- AE Listing 7 Serious Device or Procedure Related AEs
- AE Listing 8 Severe Device or Procedure Related AEs

Discharge status will be described with counts and percentages.

Evaluation of the extent of any relationship between adverse event rate to operator experience will be evaluated. Operator experience will be evaluated by credentialing the investigators by years of training, number of aneurysms treated endovascularly in the last two years.

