### **8.5 Subgroup Analysis**

Selected adverse event rates will be provided for subgroups including wide-necked ruptured versus unruptured intracranial aneurysms.

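### The site (8.7) and operator-experience (8.2) safety analyses make no adjustment for rupture status, so differences in case mix can be mistaken for differences between users

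*Combined protocol and SAP*

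**What the plan says.** Section 8.7 gives its purpose as follows: "An objective of this study is to evaluate variability in outcome among ‘real world’ users". Three per-subject endpoints are used, so that "any serious event, any device-related event, and any serious device-related event will be stratified by investigational site". If the data suffice, "the site stratified event rates will be subjected to a random effects analysis on arcsine transformed proportions". No covariate is named. Two rules apply to the result: "Sites contributing fewer than 5 subjects will be pooled", and, for I², "Fractions of 25% and less are considered small and not clinically significant". The section closes with a follow-up step: "If these analyses reveal specific sites that are outliers, further quantitative and qualitative analyses will be performed to investigate potential reasons".

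The secondary safety endpoint (3.1) is covered in 8.2 by one sentence, "Evaluation of the extent of any relationship between adverse event rate to operator experience will be evaluated", and by two measures of experience: years of training and the recent number of aneurysms treated endovascularly. No model, test or covariate is given.

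Rupture status enters the analysis only in 8.5: "Selected adverse event rates will be provided for subgroups including wide-necked ruptured versus unruptured intracranial aneurysms". It is not crossed with site or operator. Section 6.2.1 admits both types, and no section sets a quota or cap on either. Section 5.1.1 plans 90 subjects at up to 30 centers, with at most 13 at any one.

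**The concern.** Both analyses are meant to say something about users. A crude site or operator comparison does so only if the patients are comparable. The plan itself treats rupture as prognostically important: 1.1 describes death or disabling deficit in most patients with a rupture, 5.1.1 calls acute rupture emergent, and 8.5 makes it the named split for adverse events. Nothing in the design balances it across sites or operators.

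A site that takes more ruptured cases can therefore show more serious events with no difference in how the device is used. The same holds for a group of operators. The error can run either way: case mix can create an apparent user effect or hide a real one. At stake are the reading of I² against the 25% line, the labelling of a site as an outlier, and the direction of the operator-experience result.

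**Working it through.** **Plan's own figure.** The plan gives no sample size or power for these two analyses. Its only such figure is for the primary effectiveness test in 8.1. With p0 = 0.697, p1 = 0.826, one-sided 0.025 and 80% power, n = [1.96·√(0.697·0.303) + 0.842·√(0.826·0.174)]² / 0.129² = 89.4, rounded up to 90; power at 90 is 80.3%. It reproduces, and it says nothing about precision by site or operator.

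**Inputs.** From the documents: the arcsine scale, I² = t²/σ², the 25% line and the cap of 13 per site. Assumed, because the documents give none: event rates by rupture status and the ruptured share by site and operator. Throughout, rupture-specific event rates are the same at every site and for every operator, so the true user effect is nil.

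**Sites.** Site rate p = m·r + (1 − m)·u, where m is the ruptured share, r the ruptured event rate and u the unruptured rate. On the arcsine square-root scale the sampling variance is about 1/(4n), so I² = t²/(t² + 1/(4n)).

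With u = 10%, r = 40%, half the sites at 10% and half at 70% ruptured:
- site rates are 0.1·0.40 + 0.9·0.10 = 0.13 and 0.7·0.40 + 0.3·0.10 = 0.31;
- t² = 0.0123;
- at n = 10 the sampling variance is 1/40 = 0.025;
- I² = 0.0123/(0.0123 + 0.025) = 33%.

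The same calculation for other assumptions (u = 10%):

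| Ruptured event rate | Shares 10%/70%, n = 10 | Shares 10%/70%, n = 13 | Shares 20%/60%, n = 10 |
|---|---|---|---|
| 20% | 7% | 9% | 3% |
| 40% | 33% | 39% | 18% |
| 50% | 44% | 51% | 25% |
| 60% | 53% | 60% | 33% |

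At 5 subjects per site, the 40% case with shares of 10%/70% gives 20%. Case mix alone can cross the plan's line, but it needs both a clear contrast in event rates and a clear imbalance in mix.

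**Noise in I².** I² was simulated on the arcsine scale (20,000 trials per setting, weights 4n, I² = max[0, (Q − df)/Q]) with r = 40% and u = 10%. The table shows the proportion of trials with I² above 25%.

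| Layout | Same ruptured share (40%) everywhere | Shares 10%/70% |
|---|---|---|
| 9 sites of 10 | 52% | 80% |
| 7 sites of 12-13 | 37% | 73% |
| 15 sites of 6 | 74% | 91% |

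No site here has fewer than 5 subjects, so the pooling rule does not come into play. Even with no case-mix difference, I² passes the line in roughly a third to three quarters of trials, depending on layout. Case mix adds to a statistic that is already hard to read.

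**Operators.** Suppose one group has a higher ruptured share than the other, with u = 10%:
- r = 40%, shares 55% v 25%: rates 0.265 v 0.175, odds ratio (0.265/0.735)/(0.175/0.825) = 1.70.
- r = 40%, shares 50% v 30%: rates 0.25 v 0.19, odds ratio 1.42.
- r = 25%, same two pairs of shares: odds ratios 1.40 and 1.25.
- A stronger case, r = 50%, shares 60% v 20%, 45 subjects per group: rates 0.34 v 0.18, odds ratio 2.35, and a 41% chance of p < 0.05. With r = 20% this falls to an odds ratio of 1.40 and an 8% chance.

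In every case the true odds ratio is 1.

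**The case against.** Five arguments weigh against the point.

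1. Section 8.7 promises further analysis of outlier sites, and case mix is an obvious reason to look for. This stands in part. The step is post hoc, names no variable, starts only once a site is flagged, cannot uncover a user effect that case mix has masked, and does not reach 8.2.

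2. A reader might infer that the plan has chosen a crude operator analysis. The documents do not support that: 8.2 is unspecified. The gap there is a missing model, with rupture status the first covariate to name.

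3. Two of the three endpoints in 8.7 are device-related. The relatedness criteria in 11.2 ask whether the subject's clinical state could have produced the event, and under 11.3 the DSMB adjudicates relatedness of all serious events. Both filter out some rupture-driven events. This stands: the concern falls mainly on any serious event.

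4. The event rates and mixes are assumed. This also stands. The figure in 1.1 describes outcome after rupture, not adverse events after this procedure. A reader might also infer that experienced operators take more ruptured cases and so will look worse; nothing in the documents says so.

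5. The consequence is limited. The random-effects analysis runs only if data suffice, no success criterion depends on it, and operator experience is a secondary endpoint. Given the noise in I², adjustment alone would not make 8.7 precise. That argues for exploratory labelling, not for leaving a known confounder out.

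**Conclusion.** The point holds: neither analysis accounts for rupture status, and the separate rates in 8.5 do not fill the gap. Differences in ruptured share between sites or operators can be mistaken for user effects. The stronger statement, that they will be, is not supported. It needs unequal mix together with unequal event rates, and the documents give neither.

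Under the stated assumptions the effect ranges from negligible (I² of 3-7% with a ruptured rate of 20% at 10 per site) to enough to cross the plan's line (33% with a ruptured rate of 40% and shares of 10%/70%). For operators, a crude odds ratio of 1.4-1.7 can arise with no true effect when the ruptured rate is 40%. I am confident of the omission. Its size in this trial is unknown until the ruptured share by site and operator is seen.

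**What to change.** In 8.7, keep the planned arcsine analysis as the crude description. Add a subject-level logistic mixed model with a random site effect and rupture status as a fixed covariate. A subject-level covariate cannot enter a model of site-level proportions; if the sponsor prefers to stay on the arcsine scale, use each site's ruptured share as the covariate instead. List that share beside the site's crude rate. I would not ask for forest plots split by rupture status, because with at most 13 subjects per site the cells would be nearly empty.

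In 8.2, state the model: logistic regression of the adverse event endpoint on the experience measure, adjusted for rupture status, with the crude rates also shown.

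Label both adjusted analyses exploratory given N = 90, and fix them before results are seen.

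Cost: one additional model for 8.7, one extra parameter in each analysis, and slightly wider intervals. Rupture status is already needed for 8.5, so no new data, visit or subject is required.

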## **5. SITES AND SUBJECTS**

### **5.1 Subjects**

#### **5.1.1 Enrolment and Informed Consent**

Ninety (90) subjects with device deployment will be enrolled in up to 30 US clinical centers, while no more than 13 subjects should be enrolled at each clinical center.

Subject's informed consent must be obtained and documented according to the principles of informed consent.

Any subject who is consented for endovascular treatment of an IA that may potentially require use of the Comaneci device at the participating centers in the study will be approached for consenting prior to device use, using separate consent for the subject's participation in and data collected to be included in the SUCCESS study.

Subjects with ruptured aneurysms: due to the emergent nature of acutely ruptured aneurysms, informed consent may be obtained from the point of arrival at the medical treatment facility up to 72 hours after the study procedure.

For all subjects, consent must be obtained before any data is captured in the eCRF. Accounting for all unsealed Comaneci devices in each IA case that may potentially require use of the Comaneci device at a clinical site for the period of enrollment to the study will be provided. The accounts will not provide patient information but will provide some indication of the device disposition.

A patient informed consent form (ICF) will be given to each Subject or their Legally

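### Section 8.7 treats an I² of 25% or less as clinically unimportant, but I² is a share of variance that depends on site size and cannot measure clinical importance

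*Combined protocol and SAP*

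**What the plan says.** Section 8.7 opens with the purpose: "An objective of this study is to evaluate variability in outcome among" real-world users. Three summary endpoints are taken by site: "any serious event, any device-related event, and any serious device-related event will be stratified by investigational site". The modelling step is conditional: "If there is sufficient data, the site stratified event rates will be subjected to a random effects analysis on arcsine transformed proportions". Small sites are merged: "Sites contributing fewer than 5 subjects will be pooled".

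Site effects are assumed normal with variance t². The section then states "The quantitative measure of the magnitude of heterogeneity is" I², defined as t² divided by total variance, that is, the part of site-to-site variance not due to sampling. The rule at issue follows: "Fractions of 25% and less are considered small and not clinically significant". A forest plot and further analysis of outlying sites are also planned.

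Section 5.1.1 sets the scale: "Ninety (90) subjects with device deployment will be enrolled in up to 30 US clinical centers", with a cap of 13 per center. Neither section defines a clinically important difference between sites in event rate. No interval for I² or t² is planned, and neither the arcsine variant nor the estimator is named.

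**The concern.** Calling a fraction small is a convention. Calling it clinically unimportant is a claim about patients, and a ratio of variances cannot support it. When sites are small, sampling variance is large, and a wide spread of true event rates can still be a small share of the total. The rule then returns a reassuring label because the sites are small, not because they are alike.

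At stake is how the report describes variation in serious and device-related events between users, which 8.7 names as an objective. A reader could be told that site differences are clinically unimportant when the data cannot show it.

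**Working it through.** **Inputs.** From the documents: 90 subjects, up to 30 centers, at most 13 per center (5.1.1); sites under 5 pooled, arcsine scale, I² = t²/σ², cutoff 25% (8.7). Unpooled sites therefore have 5 to 13 subjects. With all 30 centers active the average is 90/30 = 3, so the pooled stratum may be large. Assumed, because the documents give none: event rates and site layouts.

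**The plan's own figures.** The 25% cutoff has no derivation to reproduce. The total that fixes site size does reproduce: with 69.7% against 82.6% and one-sided 0.025, n = [(1.96·√(0.697·0.303) + 0.842·√(0.826·0.174)) / 0.129]² = 89.4, so 90.

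**Step 1: same rate difference, different I².** The large-sample variance of arcsin√p is 1/(4n). With half the sites at rate a and half at b, t² = [(arcsin√b − arcsin√a)/2]² and I² = t²/(t² + 1/(4n)).
- 5% and 15%: t² = [(0.3977 − 0.2255)/2]² = 0.00741.
- 10% and 30%: t² = [(0.5796 − 0.3218)/2]² = 0.0166.

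| Subjects per site | 1/(4n) | I², 5% vs 15% | I², 10% vs 30% |
|---|---|---|---|
| 5 | 0.0500 | 13% | 25% |
| 10 | 0.0250 | 23% | 40% |
| 13 | 0.0192 | 28% | 46% |
| 100 | 0.0025 | 75% | 87% |

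Down each column the difference in event rates is unchanged. Only the site size moves I² across the cutoff.

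**Step 2: what an I² of exactly 25% allows.** Setting t²/(t² + 1/(4n)) = 0.25 gives t² = 1/(12n). With a typical rate of 10% (arcsin√0.10 = 0.3218), the middle 95% of true site rates is sin²(0.3218 ± 1.96t).
- n = 5: t = 0.129, range 0.5% to 30%.
- n = 10: t = 0.091, range 2.0% to 23%.
- n = 13: t = 0.080, range 2.7% to 21%.

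Section 8.7 labels all of these clinically unimportant.

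**Step 3: precision of an observed 25%.** For k equal sites, Q(1 − I²) follows a chi-square on k − 1 degrees of freedom, and an observed 25% means Q = (k − 1)/0.75. The upper 95% limit is 1 − χ²(0.025)/Q. For 7 sites this is 1 − 1.24/8 = 85%; for 18 sites it is 1 − 7.56/22.67 = 67%. The lower limit is 0 in both. The simpler test-based formula gives upper limits of 67% and 58%.

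**Step 4: the unnamed variant.** This step assumes the usual large-sample variances, 1/(4n) for plain and 1/(4n+2) for double arcsine, and I² = max(0, (Q − (k−1))/Q). Simulation used 40,000 trials and 90 subjects.

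| Layout | 5% vs 15%, I² ≤ 25%: double | 5% vs 15%, I² ≤ 25%: plain | All sites 10%, I² > 25%: plain | Expected by chance |
|---|---|---|---|---|
| 7 sites of 12–13 | 58% | 17% | 66% | 24% |
| 9 of 10 | 71% | 17% | 71% | 22% |
| 15 of 6 | 96% | 34% | 59% | 18% |
| 18 of 5 | 99% | 45% | 45% | 16% |

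These layouts have no pooled stratum. An uneven 16-site layout with its eight smallest sites pooled gives 67% in the plain-arcsine column for identical sites. Ten sites of 9 give 76%, so the ranges depend on layout. For 10% vs 30%, I² is 25% or less in only 4–17% of trials with plain arcsine, and in 28–71% with double arcsine.

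Double arcsine mainly hides the 5% vs 15% difference. Plain arcsine mainly signals differences that do not exist.

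**The case against.** The best defense is that nothing turns on the cutoff. The model is run only if data suffice, site-stratified rates are reported regardless, and outlying sites are followed up whatever I² shows. Section 3 does not list site variability among the study objectives; only 8.7 does. All of this stands and limits the severity. None of it makes the label correct.

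Three stronger readings are tempting, and the documents do not support them.

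- *The rule hides threefold differences in general.* It does so for 5% against 15% at small sites. It does not for 10% against 30%, where true I² is at or above about 25% throughout the range of 5 to 13.
- *The plan uses a wrong variance formula.* It states none, and it names neither variant nor estimator. The gap is that they are unspecified. The plan's remark that under a normal site distribution "sensitivity to small sample sizes in individual sites is reduced" does not claim to correct within-site variance, so it is not an error on that ground.
- *The report could both miss real differences and raise false ones at the rates shown.* The variance understatement that inflates I² with plain arcsine also reduces masking, so the two harms do not occur together at full size.

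**Conclusion.** The point holds as a minor correction. The label in 8.7 is not supported by the statistic it is attached to, because I² as the plan defines it depends on site size. At 5 to 13 subjects per site, a true I² of 25% is compatible with site event rates from about 0.5% to 30% (n = 5) or 2.7% to 21% (n = 13), given an assumed typical rate of 10%. How often a real difference would be labelled unimportant depends on the event rate, the layout and the arcsine variant: for 5% against 15%, from 17–45% of trials (plain) to 58–99% (double) in the four layouts. With no site differences at a 10% rate, plain arcsine exceeds 25% in about 45–71% of trials in those layouts, against 16–24% expected by chance.

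The dependence on site size follows from the plan's definition alone. The percentages rest on assumed rates and layouts, and the simulated ones also on the usual large-sample variances and a Q-based I². A large pooled stratum would change them. A reader might infer that the primary analyses are affected; they are not. The risk is a misleading summary sentence.

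**What to change.** In section 8.7:

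1. Delete the sentence containing "Fractions of 25% and less are considered small and not clinically significant", or at least its clinical claim.
2. Report the between-site variance, or I², with a 95% interval, and preferably the range of site event rates that it implies.
3. Add: *A low or zero estimate does not show absence of site differences.*
4. Name the arcsine variant and the estimator.

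Keep the site-stratified rates, forest plot and outlier review.

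Optional, as a sensitivity analysis only: a random-intercept logistic model, or a simulated or permutation reference for Q at the actual site sizes. A permutation reference alone gives a p-value, not an interval. Neither should be presented as a required replacement. At assumed event rates of 10–15% and a true between-site SD of 1.0 on the log-odds scale, power is only 20–37% for the logistic test and 22–45% for the permutation reference.

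The cost is wording plus standard output from the software already planned, with no new data. The downside to state openly is that intervals will be wide and power to detect site differences is low.

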### **8.8 Deviations from the Statistical Plan**

Any departure or deviation from these planned statistical methodologies will be documented and discussed in the Clinical Study Report summarizing the results from this study.

### **8.9 Software**

Statistical analyses will be performed using SAS version 9.4 or later and/or R version 3.4 or later.

## **9. RISK/BENEFIT ANALYSIS**

This is an observational study only; therefore, data collection does not introduce additional risks to the patients, apart from the procedure’s possible risks.

The IFU attached as Appendix A, describes the procedure’s potential complications and technical success analysis.

---

Higgins JPT and Thompson SG. Quantifying Heterogeneity in a Meta-Analysis. Statistics in Medicine 21(11): 1539-1555.

